### **2.5. Conduct of the study**

#### **2.5.1. Data collection**

Following patient recruitment, medical history taking, and physical examination, all included preterm infants will undergo two nocturnal continuous recordings of ECG, SpO2 and respiratory movements between 9:00 pm and 9:00 am. The two 12-hour recordings will be performed at 48-hour interval—i.e., with a 24-hour wash-out period—, one in the control condition, and the other under vanilla odor exposure, in a random order and in a balanced fashion.

#### **2.5.2. Polysomnographic recordings**

In addition, two 3-hour polysomnographic recordings will be performed on the morning following the 12-hour recordings above in a convenience subsample of 10 to 15 of the infants —depending on the availability of the research personnel—. These additional recordings will allow gathering preliminary results on the potential effect of vanilla odor on sleep-wakefulness cycles.

### **2.6. Data analysis**

#### **2.6.1. Variables**

In agreement with our main research question, we will compute the 90% and 80% desaturation indices per hour from the two 12-hour nocturnal recordings. We will also compute the percentage of the recording time spent with  $\text{SpO}_2 < 80\%$ , the percentage of the recording time spent with  $\text{SpO}_2 < 90\%$ , the percentage of the recording time spent in periodic breathing and the bradycardia index per hour.

Finally, a corollary study will be performed by a physiology doctoral student under the direction of [name] to assess the effect of vanilla odor on heart and respiratory rate variability. This assessment will be performed on the 12-hour recordings and will not require any additional intervention on the preterm infants.

### **2.6.2. Definitions**

- States of alertness: the usual electrophysiological and behavioral criteria will be used to recognize wakefulness, NREM and REM sleep (Anders et al, 1984; Grigg-Damberger M et al, 2007).
- Central apneas will be defined by the absence of both nasal airflow and respiratory movements for at least two respiratory cycles, if a desaturation  $\geq 3\%$  or an arousal is present, or for 20 seconds in the absence of desaturation or arousal (Nunez J et al, 2011; Henderson-Smart DJ et al, 1986).
- Periodic breathing: an epoch of periodic breathing will be defined by the presence of at least three central apneas with a duration  $\geq 3$  seconds, with a maximum of 20 seconds of normal respiration between two apneas (Brockmann PE et al, 2013).
- Desaturation: a desaturation will be defined as a decrease in  $\text{SpO}_2$  below 90% and of at least 5% compared to the preceding  $\text{SpO}_2$ , for a duration  $> 5$  seconds (Rhein et al, 2014).
- Bradycardia: a bradycardia will be defined as a decrease of at least 33% in heart rate for  $\geq 5$  seconds (Poets et al, 1993).

### **2.7. Statistical analysis**

Statistical analysis of the results has been elaborated with [name], biostatistician at the University of Sherbrooke Hospital Research Center. For each continuous quantitative variable, the normality of the distribution will be first confirmed with the *Shapiro-Wilks* test. Then, a mixed model will be designed with the SPSS software and used under close supervision of [name].

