# **Effect of Vanilla on Hypoxic Intermittent Events in Premature Infants**

**NCT02630147**

**Protocol version 1.0**

**April 13, 2015**

## 1. OBJECTIVES AND HYPOTHESIS

### 1.1. Main objective

The main objective of the study is to assess whether exposure to vanilla odor decreases the number of intermittent hypoxia events in preterm infants born between 32 and 33 weeks and reaching near term-equivalent age. A hypoxic event is defined as a desaturation < 90% with a decrease in oxygen saturation ( $\text{SpO}_2$ )  $\geq 5\%$  compared to preceding  $\text{SpO}_2$ , for a duration  $\geq 5$  seconds (Rhein et al. 2014).

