## 2. METHODS

### 2.1. Study design

To fulfill our main objective, a randomized, controlled, unblinded, balanced cross-over study will be performed.

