#### 2.2.1. Patient sample

We will study a convenience sample. Preterm infants in the neonatal care unit will be included in chronological order of their birth.

The sample size has been computed with the help of [name], biostatistician at the University of Sherbrooke Hospital Research Center using the *nQuery* software. Literature data suggest that an average of 4 periodic breathing epochs per hour is expected in the population under study (Martin et al, 2011). A sample of 17 patients is therefore necessary to detect a difference of 33% between conditions, with a power of 80% and an  $\alpha$  error of 0.05. Accordingly, we aim to include 30 preterm infants to get 20 technically valid recordings. If necessary, we will continue patient recruitment to reach 20 valid recordings. We believe that the latter can be obtained within a 2-year period. This number is based on data from the neonatal care unit at the University of Sherbrooke Hospital Center showing that 51 and 59 preterm infants were born between 32 and 33 weeks in 2012 and 2013 respectively.

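### Does the Shapiro-Wilk step in section 2.7, with no stated action on failure and no written model, have to be replaced by one fixed model and scale?

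*Combined protocol and SAP*

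**What the plan says.** Section 2.7 (Statistical analysis) is the whole statistical plan. Its first analytic step is "For each continuous quantitative variable, the normality of the distribution will be first confirmed with the" Shapiro-Wilk test. Next, "Then, a mixed model will be designed with the SPSS software", with the same biostatistician supervising its use. The section also states that "Statistical analysis of the results has been elaborated with" that biostatistician, so the approach was discussed in advance, although the resulting model is not recorded.

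Three other places matter:

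- Section 1.1 sets the question, whether "exposure to vanilla odor decreases the number of intermittent hypoxia events in preterm infants", and section 2.6.1 gives the measured form: "we will compute the 90% and 80% desaturation indices per hour from the two 12-hour nocturnal recordings".
- Section 2.1 gives the design: "a randomized, controlled, unblinded, balanced cross-over study will be performed". Section 2.5.1 adds that each infant has one control night and one vanilla night, in random and balanced order.
- Section 2.2.1 plans for losses: "we aim to include 30 preterm infants to get 20 technically valid recordings", and "If necessary, we will continue patient recruitment to reach 20 valid recordings".

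No section names the fixed or random effects, the outcome scale, or a fallback. The text also does not say whether normality is checked on raw values, within-infant differences or residuals.

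**The concern.** The wording assumes that normality will be confirmed, and hourly desaturation counts in preterm infants are likely to be skewed. If the test rejects, the plan has no next step. On the natural reading it tests raw values, whereas the condition effect in a cross-over rests on within-infant differences, from which each infant's own level cancels. For example, with skewed infant means and normal night-to-night noise, simulation has Shapiro-Wilk rejecting the control night in 22-77% of trials, although the differences are exactly normal and the paired test holds its 5% level (5.0-5.4%).

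The order of the two sentences adds to the worry, since the model is designed after the distribution has been seen, in an unblinded study. If raw, log and rank analyses gave different verdicts, a reader could not tell a planned analysis from a chosen one. Period is also not mentioned. If losses left the two sequences unequal and the second night differed from the first, an analysis without a period term would be biased.

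**Working it through.** **Inputs.** From the documents: two 12-hour nights per infant, 20 valid infants sought from 30, a 33% difference, 80% power, alpha 0.05, N = 17, and 4 per hour (section 2.2.1, where it is a periodic-breathing rate; no desaturation rate is given). Assumed: log-normal variation between infants (CV 0.3 to 1.0) and between nights (CV 0.2 to 0.5), Poisson counts, and a true rate ratio of 1 or 0.67. Sidedness is not stated; two-sided is assumed.

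**1. The plan's own figure.** The difference is 0.33 × 4 = 1.32 per hour. N = 17 cannot be reproduced directly because no SD is stated. A two-sided paired t test with N = 17 and 80% power needs a standardized difference of 0.724, so the SD of differences would be 1.32 / 0.724 = 1.82 per hour. At that SD, the usual cross-over model (condition, period, sequence, infant) tests on N − 2 rather than N − 1 degrees of freedom:

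- N = 17: power 79.7% against 80.0%.
- N = 20: power 86.4% against 86.6%.

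The standard model fits within the planned sample.

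**2. Is normality often rejected, and does that harm the error rate?** Simulation with no treatment effect, 20 infants, 4 per hour, 8,000 trials per row (Monte Carlo error √(0.05 × 0.95 / 8000) = 0.24 points). All entries are percentages; the last five columns are type I error.

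| CV between / night | Either night rejected | Raw | Log | Wilcoxon | Log if rejected, else raw | Smallest p of three |
|---|---|---|---|---|---|---|
| 0.5 / 0.3 | 77.5 | 4.6 | 4.8 | 4.7 | 5.1 | 7.0 |
| 0.5 / 0.5 | 90.6 | 4.3 | 5.3 | 5.0 | 5.5 | 7.7 |
| 1.0 / 0.3 | 95.6 | 3.8 | 4.9 | 5.0 | 5.1 | 7.7 |
| 1.0 / 0.5 | 98.3 | 3.5 | 5.2 | 4.9 | 5.2 | 8.2 |

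Rejection is common, but every single route lies between 3.5% and 5.5%. Switching to Wilcoxon after rejection gives 4.5-5.4% over rates of 1 to 4 per hour (CVs 0.5/0.3 and 1.0/0.4). Removing the test therefore gains nothing in error rate.

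**3. Can the unstated branch decide the verdict?** At a true ratio of 0.67, among trials where either night is rejected:

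- Raw, log and Wilcoxon do not all agree on p < 0.05 in 9-29% (CVs 0.5/0.3 and 1.0/0.4, 1 to 4 per hour).
- Once normality is rejected, the natural fallbacks are log and Wilcoxon. These two disagree in 5.5% and 15% at 4 per hour, and in 12% and 19% at 1 per hour.
- At lower variability (0.3/0.2), log and Wilcoxon disagree in about 0-6%. At 4 per hour either night is rejected in 47% of trials, and all three methods disagree in 0.8% of those.

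**4. Scale.** Period-adjusted power, log against raw:

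- Proportional effect, 4 per hour: 93.0% against 89.5%, and 74.1% against 57.7% (gains of 3.5 and 16.4 points).
- Proportional effect, 1 per hour: 70.1% against 72.4%, and 50.7% against 46.4% (−2.3 and +4.3).
- Additive effect of 1.32 per hour: 72.9% against 86.6%, and 66.5% against 85.6% (−13.7 and −19.1).

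A 33% difference fits either a ratio of 0.67 or a shift of 1.32 per hour, so the documents do not settle the scale.

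**5. Period.** At 10:10 a period effect cancels from the estimate. At 12:8, without a period term, a share (12 − 8)/20 = 0.2 of it remains. For an assumed 20% fall on night 2, exp(0.2 × ln 0.8) = 0.956, so a ratio of 0.67 reads as 0.67 × 0.956 = 0.64 or 0.67 / 0.956 = 0.70, depending on which sequence is larger. A split of 12:8 or worse has probability 24.5% if 20 of 30 (15:15) are valid at random, and 0% if losses are replaced within sequence. The plan does not exclude a period term.

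**The case for a change.** The strongest case for change is that the plan should state one analysis before data are seen, and it does not. The unwritten branch may be the expected path, the methods can disagree in up to 29% of the trials that reach it, the study is unblinded, and a few sentences would close the gap without one extra infant.

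The factual part stands: the terms, scale and fallback are not recorded anywhere. The disagreement is also real when variability is high.

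The inference to a faulty analysis is weaker:

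- The 29% counts the raw analysis as a candidate after normality has been rejected. Without it the upper figure is 19%, and it falls to a few percent at low variability.
- Disagreement between valid methods near the 5% boundary is not bias. Inflation needs deliberate selection of the smallest p value.
- Testing raw values is the natural reading of section 2.7, but not the only one.
- The period argument needs both an undocumented difference between nights 48 hours apart and unequal losses in a design stated to be balanced.
- Fixing one scale now means choosing between a gain of 3-16 points and a loss of 14-19 on no data.
- Putting a paragraph on the 90% index in place of the two sentences would remove the only analysis stated for the other variables in section 2.6.1.

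**Conclusion.** No change is called for. Section 2.7 is brief, and what it omits is routine. A two-condition, two-night randomized cross-over points to condition, period, sequence and infant, and the biostatistician who helped plan the analysis is to supervise the fit. If normality fails, a log or rank analysis is the ordinary response, and either keeps type I error near 5% (3.5-5.5% across the single routes tabulated). The excess, to 7.0-8.2%, requires choosing the best of three p values. The period term costs almost nothing and remains open to the analyst; the scale is a fair trade-off.

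What remains is a limit on how firmly a reader can call the analysis pre-specified. It is not an error that makes the result wrong. This rests on assumed variances (between-infant CV 0.3-1.0, night CV 0.2-0.5), on rates of 1 to 4 per hour, of which the 4 is a periodic-breathing figure, and on the expectation that the supervising statistician fits the model that the design implies.
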